In order to understand which components of social capital are most important for YBMSM and engagement in care, we will draw on quantitative data that is currently being collected with YBMSM in our clinic. [name] successfully competed for a developmental grant from the Emory Center for AIDS Research (CFAR), in which she is beginning to explore social capital among YBMSM at the IDP clinic. The study has a cross-sectional design and participants' involvement involves a single study visit in which they complete an ACASI including our modified social capital scale (MSCS). We also obtained the participants' permission and abstracted data for each patient with respect to appointment adherence, and viral suppression. We can therefore measure associations between engagement outcomes and various dimensions of our social capital measure.

Measure: There is no existing published scale for social capital which has been validated in a United States youth population or in YBMSM more specifically. However, as mentioned above, we have recently modified, pilot tested, and validated Chen's Social Capital Scale to create the MSCS (that we will use in this study). Although Chen's original scale addressed conceptual domains of interest (bonding social capital, bridging social capital, and collective efficacy), it was developed for use among adults in China and therefore contained items that were not culturally relevant to YBMSM. Our MSCS had excellent reliability in an online sample of YBMSM ($\alpha=0.88$; data not yet published). The scale contains subscales for bonding and bridging capital, and it also contains items that specify sources (including family, friends, and LGBT organizations) and types of support (e.g. emotional support, instrumental support and informational support). We can therefore determine which components of individuals' networks are most related to care engagement outcomes using our cross-sectional data.

Sample Size: 80 HIV-positive YBMSM in care at the Grady IDP clinic

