4.1 VARIABLES/INTERVENTION

4.2 Variables

Table 2: Variables and Measures

	Method of Measurement	Number of items	Timeline
Social Capital (Primary Outcome)	Modified Social Capital Scale (based on Chen, et al.) ¹⁶	10	Phase I: Analysis of previously collected data Phase III: RCT participants at 0, 1, 4 and 10 months

	Qualitative Interviews	n/a	Phase I: In-depth interviews with YBMSM living with HIV Phase III: Pre- and post-intervention interviews
Engagement in HIV Care (Secondary Outcomes)			
Viral load suppression	Electronic medical record abstraction	n/a	Phase III: RCT participants at baseline, post-intervention and 10 months (if available; see page 17 for more detail)
Retention in Care	Electronic medical record abstraction	n/a	Phase III: RCT participants at 0 and 10 months
Antiretroviral adherence	Single item self-report ⁵²	1	Phase III: RCT participants at 0 and 10 months
Correlates (measuring other factors shown to relate to engagement in care among YBMSM in prior work)			
CD4 count (recent and nadir)	Electronic medical record abstraction	n/a	Phase III: RCT participants at baseline and post-intervention 10 months (if available; see page 17 for more detail)
Demographics	Survey questions	23	Phase III: RCT participants at 0, 1, 4 and 10 months
Depression	CES-D ⁵³	20	Phase III: RCT participants at 0, 1, 4 and 10 months
HIV Stigma	HIV Stigma Scale ⁵⁴	10	Phase III: RCT participants at 0, 1, 4 and 10 months
Ethnic Identity	Multi-Ethnic Identity Measure ⁵⁵	12	Phase III: RCT participants at 0, 1, 4 and 10 months

Gay Identity	Internalized Homonegativity Inventory ⁵⁶	23	Phase III: RCT participants at 0, 1, 4 and 10 months
Drug Abuse	CAGE-AID ⁵⁷	4	Phase III: RCT participants at 0, 1, 4 and 10 months
Social Support	Zimet's Multidimensional Social Support Scale ⁵⁸	12	Phase III: RCT participants at 0, 4 and 10 months
Group Dynamics	Selected items from Schulz, Israel and Lantz ⁵⁹	20	Phase III: RCT participants at 0, 1, 4 and 10 months
Social Networks	Lubben Social Network Scale	6	Phase III: RCT participants at 0, 4 and 10 months
Engagement with Health Care Provider	HCP Scale	13	Phase III: RCT participants at 0, 4 and 10 months
Identification and Involvement With the Gay Community	Identification and Involvement With the Gay Community Scale	8	Phase III: RCT participants at 0, 1, 4 and 10 months
General Wellbeing	The General Well-Being Schedule (GWB)	18	Phase III: RCT participants at 0, 1, 4 and 10 months

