Psychological Distress	Brief Symptom Inventory	53	Phase III: RCT participants at 0, 4 and 10 months

Outcome Measures: The primary outcome measure will be social capital. The core measure of social capital that we will use is our Modified Social Capital Scale (MSCS) described above, which we developed and validated exclusively with YBMSM. Our aim is to discover whether social capital improves as a result of being in the social capital intervention, and also to see if there is any similar effect in the control arm. Secondary outcomes will be measures of HIV care engagement, namely: (1) Retention in care, (2) Adherence to medications, and (3) HIV viral load suppression. As per Institute of Medicine (IOM) recommendations, **retention in care** will be measured by determining, within the 10 months of the study period, (a) participation in continuous care, that is, at least two or more routine HIV visits at least three months apart, (b) receiving two or more CD4 tests, and (c) receiving two or more viral load tests.⁶⁰ **Adherence to antiretroviral medications** will be measured using a composite of single item self-report question and pharmacy refill records. **HIV viral suppression** will be considered achieved if the medical records report a viral load below the level of detection for the site-specific assay. Viral load values and appointment attendance will be extracted from the participants' EMR.

4.3 Intervention Content: As the details of the intervention will be influenced greatly by the formative research and the input of the YCAB, it cannot be described in full detail at this time. The main intervention delivery will consist of either a one day or a consecutive two day group

meeting among the YBMSM with time divided between health education and community photovoice project planning. Each group will contain ten YBMSM; we plan for six groups each in the control and intervention arms. As detailed above, the intervention will consist of a group-based curriculum in program planning and HIV education, culminating in the planning and implementation of a community photovoice project.

4.4 Outcomes: The primary outcome of interest for the RCT will be social capital, as we are aiming to determine whether or not our intervention is effective in increasing social capital. We will also look at engagement outcomes, to determine whether or not increasing social capital has an impact on care engagement in our participants.

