5.1 DATA ANALYSIS AND MANAGEMENT

5.2 Data Analysis: We will be collecting both qualitative and quantitative data during the course of this survey.

5.2.1 Quantitative analyses: Will be conducted using SAS or SPSS statistical software. An odds ratio plus the 95% confidence interval will be calculated to measure the degree of association between retention in care measures and total social capital (all analyses will also be computed for bonding/bridging subscales alone, as well as for item clusters focusing on different dimensions of social capital). Odds ratios will also be calculated to measure the degree of association between other risk factors (education, employment, age, depression, substance use, HIV stigma and CD4 cell count) and patient retention.

Additionally, total social capital will be compared between engaged and non-engaged patients using a two-sided two-sample t-test. Other potential risk factors will be compared between retained and non-retained patients using a chi-square test or Fisher's exact test for categorical covariates and a two-sided two sample t-test for continuous covariates.

Multivariable analyses: Covariates significant to at least $P \leq 0.20$ in the univariable analyses will be used in multivariable logistic regression analyses. Although empirical techniques will be used to identify important covariates, theoretical expectations from our social capital conceptual framework will also augment these decisions. Interactions between covariates will be evaluated, either because suspicions are raised by clinical judgment before the analyses are performed or by statistical examination. Forward stepwise selection will be used if necessary to choose prognostic variables for a multivariable logistic regression model. The odds ratio and its 95% confidence interval will be calculated for each risk factor in the presence of others in the final model.

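### Section 4.4 asks whether raising social capital changes care engagement, but the only written analysis relates a social capital level, at no stated time point, to retention

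*Combined protocol and SAP*

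**What the plan says.** Section 4.4 (Outcomes) names social capital as the primary outcome, then adds that engagement outcomes will be examined "to determine whether or not increasing social capital has an impact on care engagement in our participants".

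Section 5.2.1 holds the only quantitative methods. An odds ratio is to "measure the degree of association between retention in care measures and total social capital". In addition, "total social capital will be compared between engaged and non-engaged patients using a two-sided two-sample t-test". Covariates are screened at P ≤ 0.20, and "Forward stepwise selection will be used if necessary to choose prognostic variables for a multivariable logistic regression model". The same text appears in section 2.1, Part 1c, where it was written for an earlier survey of 80 men. Of that survey the protocol says: "The study has a cross-sectional design and participants' involvement involves a single study visit".

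On timing, section 4.2 defines the main retention component as "at least two or more routine HIV visits at least three months apart", counted "within the 10 months of the study period". Table 2 schedules the Modified Social Capital Scale (MSCS) for "RCT participants at 0, 1, 4 and 10 months".

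Aim 3b and section 2.3 also state an intention to test or quantify an effect on engagement in the trial. No between-arm engagement analysis is written anywhere.

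**The concern.** The question in 4.4 is causal and concerns a change: if social capital goes up, does engagement follow? The analysis in 5.2.1 is symmetric and concerns a level. An odds ratio between two variables does not say which came first. The t-test makes social capital the dependent variable and engagement the grouping factor, the reverse of the question.

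Two other explanations would produce the same result:

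- **Attendance raises social capital.** Men who keep coming to clinic meet staff, peers and support organisations. Section 2.3 itself expects bridging capital to grow through contact with community partners and study staff.
- **Differences at entry.** A level carries whatever a man brought with him. Section 5.7 accepts that men who join may already have more social capital and be better engaged, but treats this only as selection into the study.

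Neither 5.7 nor 5.9 mentions that the association could run from engagement to social capital. At stake is the trial's causal model: a positive odds ratio could be read as supporting it when social capital has no effect on engagement.

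**Working it through.** The plan gives no figure for this analysis. The sample size in section 3.5 concerns MSCS between arms, and this point does not depend on it.

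**Step 1. Order of measurement.**

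| MSCS wave | Position relative to the retention window (months 0 to 10) | Can it measure an increase? |
|---|---|---|
| Month 0 | Before | No |
| Month 1 | Inside, before most of it | Yes |
| Month 4 | Inside | Yes |
| Month 10 | At its end | Yes |

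An increase needs a post-baseline wave, and all three lie inside the window. Section 5.2.1 does not say which wave is used.

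**Step 2. Size of the problem if month 10 is used.** Inputs:

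- Men analysed: 120 × 0.87 = 104.4, taken as 104. The 120 is the trial's target. The 87% is follow-up in another trial cited in section 2.3, so using it here is an assumption.
- Retained in care: 70% (assumed). 104 × 0.70 = 72.8, so 73 retained and 31 not.
- True effect of social capital on retention: none.
- Rise in month-10 MSCS caused by being retained, d: 0.2, 0.3 or 0.5 SD (assumed range).
- Two-sided alpha 0.05 (assumed), 102 degrees of freedom.

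The noncentrality of the t-test is d × √(73 × 31 / 104) = d × 4.665. With equal SDs in the two groups, the odds ratio per SD is about exp(d).

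| d | Noncentrality | Significant | Apparent odds ratio per SD |
|---|---|---|---|
| 0.2 | 0.93 | 15% | 1.22 |
| 0.3 | 1.40 | 28% | 1.35 |
| 0.5 | 2.33 | 64% | 1.65 |

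A simulation with 4,000 trials per setting and an assumed between-wave correlation of 0.6 agrees: 16%, 28% and 62% with 70% retained, and 17%, 33% and 70% with 50% retained. With d = 0 it rejects in about 5%, so the excess comes from the reverse effect alone.

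**Step 3. Month 0 instead.** In the same simulation the month-0 score gives about 5%. That result assumes entry social capital and retention are unrelated. If they share causes, such as engagement before enrolment, the month-0 score would also be associated with retention.

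**Step 4. Would a change score alone suffice?** A model of later attendance on the 0 to 4 month MSCS change, with arm and baseline MSCS, was simulated with no social capital effect. Inputs were a 0.5 SD reverse effect, 104 men, 70% attending, and an assumed latent correlation of 0.5 to 0.7 between early and late attendance. It was falsely significant in roughly 11% to 25% of trials, depending on the settings. Early attendance raises the month-4 score and also predicts later attendance. Adding attendance in months 0 to 4 as a covariate, or using the 0 to 1 month change instead, brought the rate back to about 5%.

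**Step 5. Windows.** Starting after month 1 leaves 10 − 1 = 9 months. Starting after month 4 leaves 10 − 4 = 6 months for two visits at least three months apart, so the retention definition would need adapting.

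**The case against.** **Section 5.2.1 names no wave.** This is right, and it limits the claim. A reader might infer that the month-10 score will be used and that the rates in Step 2 describe the planned test. The documents do not say so: month 0 or month 1 is equally open. The rates are conditional on month 10. What stands is that nothing in the plan excludes that choice, and the wave could be chosen after the data are seen.

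**Section 4.4 may mean a randomised comparison.** Read with Aim 3b and section 2.3, the sentence can mean comparing engagement between arms after a programme intended to raise social capital. Reverse causation does not threaten that comparison. This reading is fair, but the comparison is not written. It would also show an effect of the programme, not of social capital itself.

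**The plan speaks only of association.** Section 5.2.1 uses the language of association and prognosis, and nowhere says its odds ratio answers 4.4. A reader might infer that a positive result will be reported as proof of mechanism; the documents support only that it could be read that way. But 5.2.1 is the only quantitative analysis offered, so no other written analysis addresses the 4.4 question.

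**The inputs are assumed.** The share retained and the size of the reverse effect have no source in the documents. The calculation shows what could happen, not what to expect.

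**Conclusion.** The concern holds in this form: followed as written, 5.2.1 cannot answer the question in 4.4. It relates a level to retention with no arm, wave, change score or time order, using a method carried over from a single-visit survey to a trial with four survey waves. This follows from the text and needs no assumed figure.

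The size depends on choices the plan leaves open. False-positive rates of about 15%, 28% and 64% require the month-10 score, 104 men, 70% retained, no true effect, and reverse effects of 0.2, 0.3 and 0.5 SD. A different wave or a smaller reverse effect would give less.

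This is a secondary question and does not touch the primary outcome. It should be corrected before analysis, because the planned surveys already allow a better-ordered analysis.

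**What to change.** In section 5.2.1:

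1. **Write the between-arm comparison for the trial.** Specify it for retention, adherence and viral suppression, adjusted for the baseline value where collected. Answer the impact-on-engagement question from it, described as an effect of the programme.
2. **Make the social capital analysis exploratory and time-ordered.** The predictor is MSCS change from 0 to 1 month. The outcome is engagement occurring after the month-1 survey. Covariates are arm, baseline MSCS and baseline engagement (prior retention and baseline suppression). Any 0 to 4 month version must also adjust for attendance in months 0 to 4 and use a retention definition that fits six months.
3. **Label the level-based results.** State that the odds ratio and t-test relating MSCS level to retention are descriptive associations, not evidence that increasing social capital changes engagement.

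The cost is analysis wording, using surveys and record abstraction already planned; visit dates must be kept so that attendance can be split by period. The downside is a shorter outcome window for this secondary analysis. The time-ordered model remains observational, because change in MSCS is not randomised, so it should be reported as mechanism only.

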The development of the social capital intervention will continue throughout the first 18 months of the award period. Intervention development will be a continuous and iterative process during this timeframe and will involve [name], her mentors and collaborators, the study team and the YCAB. We will present qualitative and quantitative data from Phase I formative research to the YCAB as it is collected and analyzed as a way of “member checking” our results. We will also solicit ideas for the social capital intervention, discussing ideas in an iterative process until we have completed development of the intervention. Finally, we will have the YCAB test out a mock intervention with our team, and give us feedback on what works or does not work well in our curriculum. We will present the intervention to the YCAB as many times as needed in an iterative fashion until the study team and YCAB are satisfied with the final product. Our YCAB will give us input on every aspect of the intervention, including timing, location, content, and process. Before we are ready to share the intervention as part of our RCT, we will standardize the intervention in a standard operating manual which will also be reviewed by the YCAB.

The social capital intervention will be a group-level, multi-session program that entails a structured curriculum and process culminating in a community photovoice project. **The specifics of the community photovoice project are yet to be determined, and will be decided on with the YCAB as a part of the formative work.** The curriculum will also include components focused on training in advocacy, HIV knowledge, and project planning.

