Again, the exact nature of the 30 day challenge and the intervention will be determined in conjunction with the YCAB over the course of Phase I intervention development. (The control groups will not participate in the 30 day challenge). The process of working on the 30 day challenge as part of the proposed social capital intervention has the potential to increase bonding social capital through the group's interactions with one another, as well as bridging social capital through meaningful connections with community partners and study staff. Finally, the act of creating and executing a community-oriented project will also increase participants' sense of collective efficacy (as measured by items in the MSCS), another important component of social capital.

Overview--Control arm: The control arm will participate in a health education intervention that will be delivered in a group, but without a specific goal of creating group cohesion or social capital. The intervention will be a modified version of "Health for Life" or H4L, which was used as a control arm intervention in a recently completed protocol of the Adolescent Trials Network which was co-chaired by [name] (University of Michigan). This intervention was specifically developed for young MSM of color and focuses on general health topics including diet, exercise, and safe sex. Details about the Health for Life program are included as Appendix G. We will modify the H4L intervention as needed based on the input of our YCAB. Similar to the intervention arm, the control participants will participate in either a one day or a consecutive two day group meeting at a convenient time and location. The exact number of sessions and format of

the intervention may be modified based in YCAB input; as with the intervention arm--it may be that the intervention can be delivered in fewer sessions, or in a retreat format, to enhance acceptability and retention. The same format and number of sessions will be used for both the intervention and control arms.

Procedures for intervention and control participants:

Tokens of appreciation: We will provide participants with two gift cards (value \$75) as a token of appreciation for their time and will also provide Metropolitan Atlanta Rapid Transit Authority passes (MARTA cards; \$5 fare for a single round-trip) if needed for transportation assistance. \$25 will be given on the first day and \$50 will be given on the second day

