Appendix A: B6 Addendum

A result of phase 1 was the development of Brothers Building Brothers By Breaking Barriers (B6), a two-day, 10-module group-level intervention. B6 does not focus exclusively on HIV, but rather takes a more holistic approach to supporting youth and developing resilience. The B6 intervention modules aim to develop resilience at the individual level (exploration of black gay identity, development of critical self-reflection and coping skills), social network level (exploring strategies for navigating family relationships) and community level (developing strategies for navigating clinical spaces and plans for community participation). Most intervention activities are interactive, in order to facilitate new social network connections (social capital) within intervention groups. In summary, our intensive CBPR approach resulted in a novel, culturally-specific intervention designed to enhance resilience by augmenting social capital among YB-GBMSM living with HIV.

Based on the aforementioned qualitative content analyses, a condensed list of key programmatic recommendations was created for incorporation into the intervention (Table 1). Participants had favorable reactions to the idea of a social capital-based resilience intervention for YB-GBMSM living with HIV. The most commonly cited recommendation was to ensure that the intervention addressed the holistic health and well-being of the participants, and did not focus too narrowly on HIV-specific content. Participants also gave feedback about the manner in which the intervention should be delivered, citing the importance of balancing entertainment with the educational objectives.

Table 1. Key Recommendations from Qualitative Interviews

Content

• Find a way to treat the whole person• Teach about finances, school, health, wellness• Empower participants with skills to get support they need• Raise awareness and pride about black gay culture and history• Address stigma, internalized homophobia• Find ways to create connectedness between YB-GBMSM• Refer participants to other resources as needed, particularly mental health
Approach

• Engage participants, make activities interactive and entertaining• Group discussions• Be nonjudgmental, sex positive, don't try to change people• Consider judicious use of social media• Meet participants where they are in terms of interest in HIV care engagement

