Using a process informed by Intervention Mapping, which is a planning approach that combines theory and evidence as the foundation for taking an ecological approach to assessing and intervening in health problems and engendering community participation (Eldredge, L. K. B., Markham, C. M., Ruiter, R. A., Kok, G., & Parcel, G. S. (2016). Planning health promotion programs: an intervention mapping approach. John Wiley & Sons.), we combined the qualitative findings, theoretical constructs and YCAB input to develop an intervention outline focused on the following overarching goals: (1) exploration of one's self and identities; (2) building bonding capital; (3) building bridging capital; and (4) sustaining connections. We used an Intervention Mapping- informed process to align the theoretical constructs of social capital and the feedback from the qualitative findings with specific intervention components and activities. Table 2 displays the intervention content and the learning goals and objectives for each of the 10 modules of the intervention.

Table 2. Intervention Course Agenda

Day 1	
Session 1	Welcome to B6
Module 1: Set the Stage	Welcome/Introductions Brotherhood Agreement Brother Bingo
Module 2: Who's on your team?	Social Capital Presentation (together we have more) Bound By Barriers
Session 2	Building Myself
Module 3: Who am I?	Worth a Thousand Words On the Flip Side Affirmation Activity
Module 4: Communicating my Needs	Love Languages Assertive Communication (Passive/Aggressive)*
Module 5: Critical Reflection/Problem Solving	Critical Reflection: What? So What? Now What?* What would you do?
Session 3	Building Bridges
Module 6: Breaking Barriers: Relationships	Who you gonna Call? Acting Out B6 Trivia Review Closing

Day 2	
Session 3 Continued	Building Bridges
Module 7: Breaking Barriers: Professional Settings	Welcome Back! Work/School Life (Critical Reflection/Problem Solving) Rep Your Clinic
Session 4	Building Bonds

Module 8: Black Gay Community	What is Black Gay Community? Role Models/Heroes Jeopardy
Session 5	Staying Connected
Module 9: Connecting the Dots	Goal Setting * Using my Social Capital (Support Web) Building the Other Brother
Module 10: My Social Capital	30 Day Challenge So I know it's real Conclusion

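### Section 4.4 promises a conclusion about social capital and care engagement, but the B6-versus-H4L comparison can only estimate the effect of the whole B6 package

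*Combined protocol and SAP*

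**What the plan says.** Section 4.4 names social capital as the primary outcome. It then gives the purpose of the engagement outcomes as "to determine whether or not increasing social capital has an impact on care engagement in our participants". That is a question about mechanism, and it goes further than asking whether the intervention changes engagement.

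The intervention that came out of the formative work is described in the B6 Addendum as a two-day, ten-module group programme. Its modules address individual resilience (identity, self-reflection, coping), family relationships, and a community level that includes "developing strategies for navigating clinical spaces and plans for community participation". The course agenda in Table 2 of the Addendum adds assertive communication, problem solving, goal setting and an activity called "Rep Your Clinic", alongside the network-building activities.

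The control arm, H4L, is described in Section 2.3 as a group health-education programme that "focuses on general health topics including diet, exercise, and safe sex". Section 2.3 matches the two arms on format and number of sessions and reserves the 30-day challenge for the intervention arm. It refers the reader to Appendix G for H4L details and allows H4L to be modified with input from the youth advisory board.

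Section 5.2.1 plans odds ratios for the association between social capital and retention, t-tests of social capital by engagement status, and multivariable logistic regression. It describes neither a between-arm comparison of engagement nor a mediation analysis.

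**The concern.** Randomisation supports a causal statement about what was randomised, which is assignment to B6 or to H4L. It does not by itself support a causal statement about one ingredient of B6. Section 4.4 makes the second kind of statement. To support it, either the arms would have to differ essentially in social capital alone, or a planned analysis would have to separate the part of the effect that passes through social capital from the rest. The plan provides neither, and the sections on bias (5.7) and limitations (5.9) do not raise the issue.

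Section 1.4 says the findings are meant to shape an intervention for use in other settings, and the timeline in Section 2.8 includes a new grant application. If engagement improved and Section 4.4 were followed as written, social capital would be credited with an effect that could have come from coping, communication, goal-setting or clinic-navigation content.

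**Working it through.** The plan gives no engagement effect to reproduce, so the check sets the texts side by side and then illustrates the consequence.

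**1. Contents of the arms, as described**

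| Feature | B6 (Addendum) | H4L (Section 2.3) |
|---|---|---|
| Group delivery, format, number of sessions | yes | matched |
| Network building | yes | no specific goal of this kind |
| Identity, self-reflection, coping | yes | not described |
| Communication, problem solving, goal setting | yes | not described |
| Clinic navigation | yes | not described |
| 30-day challenge | yes | no |

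*Not described* does not mean absent, because the H4L topic list is open-ended. The conclusion does not need it to mean absent: several B6 components beyond network building have no stated match in H4L.

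**2. What the arm contrast identifies**

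On a simple linear scale, write the arm difference in engagement as

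Δ = d + b × δ

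Here δ is the MSCS gain caused by B6, b is the change in engagement per MSCS point, and d is the effect of B6 by every other route. Section 4.4 asks about b. The randomised comparisons estimate Δ and δ, which leaves one equation with two unknowns, b and d.

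Section 3.5 plans for a 15% gain on a mean of 26.6. That is 0.15 × 26.6 = 3.99, giving 30.59, in line with the 30.6 in Table 1. Take δ = 4 and, purely as an example, Δ = 14.5 points. All three of these fit equally well:

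- d = 0, b = 14.5 / 4 = 3.6 points per MSCS point
- d = 7.25, b = 7.25 / 4 = 1.8 points per MSCS point
- d = 14.5, b = 0

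**3. Does the planned analysis close the gap?**

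The text of Section 5.2.1 repeats the plan for the pilot survey data in Section 2.1, Part 1c. It relates social capital to retention and describes no term for arm. If B6 raises both MSCS and retention by separate routes, the two will be associated in pooled data even when b = 0. People with more social capital at baseline may also be better engaged for other reasons. These odds ratios therefore do not separate b from d.

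**4. Illustration by simulation**

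Assumptions: 60 per arm, control suppression 46%, MSCS SD 7.0, B6 raises MSCS by 4 points, 4,000 runs, pooled two-proportion z test at two-sided 0.05, clustering by group ignored. The 46% is the clinic figure in Section 1.2.4 for ages 13-24 within a year of starting therapy. It is not a planning rate for this trial, which enrols ages 18-29.

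| Scenario | Mean arm difference | Runs significant |
|---|---|---|
| (a) No social-capital effect; rest of package adds 0.8 to the log-odds | 19.5 points | 59% |
| (b) Only social capital acts, 0.2 log-odds per MSCS point | 14.5 points | 37% |
| (c) Neither acts | 0 points | 5.6% |

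Hand check of (a): odds 0.46 / 0.54 = 0.852; times e^0.8 = 2.226 gives 1.896; 1.896 / 2.896 = 65.5%; less 46% is 19.5 points. In (b) the average shift is also 0.2 × 4 = 0.8 log-odds. The difference in proportions is smaller because it is averaged over the spread of MSCS scores.

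A substantial arm difference appears under both (a) and (b), and nothing in the arm contrast tells them apart. The sizes follow from the assumed inputs and are not forecasts.

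**The case against.** The strongest reply is that the design is sound and the complaint concerns one clause. Aim 3b asks about impact on social capital and on engagement, which already reads as a package question. Comparing a multi-component programme with a control matched on format and session number is a reasonable choice for a trial meant to develop and pilot an intervention. All of this stands. The comparator is not the fault; the inference written into Section 4.4 is.

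A second reply is that the clinic content may itself be social capital. "Rep Your Clinic" sits in the session titled Building Bridges, and the Addendum's goals include "2) building bonding capital; (3) building bridging capital; and (4) sustaining connections". The Addendum says components were aligned with social-capital constructs, and Section 1.2.5 lists informational and instrumental support among the mechanisms. This stands to the extent that clinic navigation cannot be called a rival route with confidence. It does not rescue Section 4.4. Coping, communication and goal setting are still bundled in, and if every component is counted as social capital, the claim becomes a package effect under another name.

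Two stronger readings are tempting and are not supported:

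- *That only the intervention arm receives care-related content.* The H4L topics in Section 2.3 are introduced as examples, Appendix G is not in the text available for review, and H4L may be modified.
- *That HIV knowledge is an unmatched ingredient.* Section 2.2 does say "The curriculum will also include components focused on training in advocacy, HIV knowledge, and project planning", but that text predates the finished curriculum, and no item in the B6 agenda carries that name. Section 2.6 expects control participants to gain knowledge about HIV too.

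Finally, MSCS at four time points would permit a mediation analysis. That is correct, but none is planned.

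**Conclusion.** The point holds in this form: an engagement difference between arms estimates the effect of B6 versus H4L and does not by itself show that increased social capital produced it. This follows from B6 being a multi-component package with no planned mediation analysis. It does not depend on whether H4L has some care-related content. It affects the interpretation of the secondary outcomes (retention, adherence, viral suppression) and leaves the primary MSCS comparison as it is.

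No size can be attached from the documents, since they give neither the effect of the other components nor the effect per MSCS point. The share of any engagement difference due to social capital could be anything from none to all of it. The simulated 19.5 and 14.5 points show only that both extremes yield visible differences under the stated assumptions.

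A reader might also infer that clinic-navigation content should be added to H4L. The documents do not support that as a correction. If that content is meant to build bridging capital, matching it could shrink the MSCS contrast, and coping, communication and goal setting would remain unmatched.

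**What to change.** Reword Section 4.4 along these lines: *The between-arm comparison of retention, adherence and viral suppression estimates the effect of the B6 package versus H4L; it will not by itself be taken as evidence that increased social capital caused the change.* Report Aim 3b in the same terms. Because Section 5.2.1 does not list that comparison, name it there.

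Rest any statement about social capital as the mechanism on a mediation analysis labelled exploratory, using the MSCS scores already scheduled at 0, 1, 4 and 10 months. State its assumptions:

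- Randomisation protects the effect of arm on MSCS and on engagement, but not the relation between MSCS and engagement.
- That relation must be assumed unconfounded given the covariates used, such as baseline MSCS and the baseline correlates in Table 2 (depression and stigma, for example).
- Coping or navigation skills changed by B6 could affect both MSCS and engagement, which would breach the assumption.
- Retention accrues over the ten months, so later MSCS scores overlap with the outcome. The 1-month score has the clearest time order.

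The cost is a narrower mechanistic claim and a little more analysis work. No new data are needed, and neither enrolment nor either curriculum changes.
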